6.4.3.2 Secondary Objectives Analyses, if applicable

Secondary Objective Analyses

Objective 2. Estimate the separate and combined effects of the two PIE intervention domains on infant intention communication.

H2a: At Posttest-1, infants in both groups will show no more than modest gains in intentional communication (Cohen's $d < .25$).

H2b: At Posttest-2, infants in both groups will show moderate increases in intentional communication compared to Baseline (Cohen's $d \geq .40$).

Analyses: This outcome variable involves counts of infant intentional communication attempts. We expect the average number of counts to be sufficiently large (eg. ≥ 8) that a normal approximation to a Poisson error distribution will be appropriate; however, if not, Poisson or negative binomial regression methods, or nonparametric approaches may be employed. The analyses for Objectives 2 and 3 will use the same framework as for our primary Objective #1, that is, to evaluate a priori contrasts of interest within a repeated measures mixed modeling framework. We will examine the contrast of Baseline to Posttest-1 scores and the contrast of Baseline to Posttest-2 scores (time effect). In addition, the models will include terms for treatment arm effects and treatment arm-by-time interactions.

Objective 3. Evaluate the differential changes in parent responsiveness following coaching on two individual Parents and Infants Engaged (PIE) intervention domains — responses to variable infant (a) sensory reactivity or (b) prelinguistic communication — as well as cumulative changes in parent responsiveness following coaching on both PIE domains.

H3a: At Posttest-1, parents in both intervention arm will show increases in responses attuned to their infants' behaviors compared to Baseline, with parents coached in the sensory reactivity domain showing more responses attuned to infants' sensory reactivity, and parents coached in the prelinguistic communication domain showing more responses attuned to infants' signals of attention focus and communicative intent.

H3b: At Posttest-2 (after coaching in both PIE domains), there will be no between-arm differences in parent responses attuned to infant sensory reactions or prelinguistic communication leads, due to increases in parent responsiveness to the newly coached domain of infant behaviors.

Analyses: See analyses for Objective 2.

Objective 4. Determine the extent to which autonomic indices of infant self-regulation change over the course of the PIE intervention.

H4a: From Pretest to Posttest-2, infants will show limited changes in autonomic indices during exposure to nonsocial stimuli (Cohen's $d < .25$), but will show moderate-sized increases in respiratory sinus arrhythmia (RSA) and decreases in skin conductance levels (SCL) during exposure to child-directed speech (Cohen's $d \geq .40$).

H4b: Infants will demonstrate small improvements in language, sensory reactivity patterns, response to joint attention, and social-communication skills over the course of the PIE intervention.

Analyses: The models for these analyses will use the repeated measures mixed modeling framework, as for Objectives 1, 2 and 3, except that the effects will be examined only at Posttest-2 (given that these measures will not be taken at Posttest-1). The models will include terms for treatment arm effects and treatment arm-by-time interactions.

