5.2.2 Secondary and Exploratory Outcome Variables

Secondary outcome variables:

The first three secondary outcome measures will be assessed at three timepoints: Baseline, Posttest 1 (after families have been randomly assigned to an intervention arm and coached in one of the two PIE intervention domains), and Posttest 2 (after families have been coached in both of the PIE intervention domains). For these measures, we are particularly interested in whether there are effects specific to the initial PIE coaching domain (sensory

reactivity or prelinguistic communication) at Posttest 1, and whether there are order effects (differences between study arms) at Posttest 2.

1. Changes in parent responsiveness to infant sensory reactivity cues. [Measured via a project-developed rating tool.] This secondary measure is included to determine whether coaching in the sensory reactivity domain yields the expected specific effects on parents' responses to infant sensory reactivity cues. Parents will be rated on a 1-7 scale for their responsiveness to sensory reactivity for each of the 4 activities included in the parent-infant interaction session, using videorecordings of these sessions. A manual will be developed to describe the rating system and the level of responsivity associated with each of the 7 points on the scale. Research assistants will be trained to reliability by supervising staff. During rating of the project videos, one of 5 rated videos will be independently rated for reliability. Raters will be blind to study arm and timepoint of participants.
2. Changes in parent responsiveness to infant prelinguistic communication cues. [Measured via a project-developed rating tool.] This secondary measure is included to determine whether coaching in the prelinguistic communication domain yields the expected specific effects on parents' responses to infant prelinguistic communication cues. Manualization, training and reliability procedures are identical to those described for the parent responsiveness to sensory reactivity measure.

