6.4 Statistical Method

6.4.1 Statistical Design

The study is designed as a randomized comparative trial with two phases. For Study Phase 1, dyads will participate in baseline assessments; then eligible, consenting families will be randomized, stratifying by child age, to one of two treatment arms. Arm1 families will participate in initial coaching on the PIE sensory reactivity (SR) domain, and Arm2 families will participate in initial coaching on the PIE prelinguistic communication (PC) domain. Families will participate in 6 weekly coaching sessions in their respective treatment arms, and return for Posttest-1. For Study Phase 2, dyads in Arm1 will receive 6 weekly coaching sessions on the PC domain, and dyads in Arm2 will receive 6 weekly coaching sessions on the SR domain. Then families will return for Posttest-2.

Comparisons of dyads assigned to Arm1 and Arm2 at Posttest-1 will allow us to estimate the separate effects of the two domains of PIE coaching, as dyads will have only been coached in one domain (responding to prelinguistic communication cues or sensory reactivity cues) prior to Posttest-1. At Posttest-2, we will get estimates of the additive effects of coaching in the second PIE domain, and be able to evaluate whether there are any effects of the order of coaching by comparing dyads in Arm1 to those in Arm2.

For analyses, we will utilize repeated measure analyses within a mixed modeling framework, to assess time and tx order effects, while accommodating missing data and optimally utilizing all available data.

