6.4.2 Sample Size Considerations

Assuming recruitment of 44 infant-parent dyads and allowing for a 9% (n=4) dropout rate, which is consistent with high retention rates (> 95%) in our prior intervention studies, 40 dyads (20 per treatment arm) will have complete data for analyses. Assuming a conventional type I error rate of .05, and intercorrelations among the repeated measures from .3 to .7, the magnitude of treatment group effects detectable with a .80 statistical power will range from $f=.37$ to $.42$, respectively, which are large standardized effects. The magnitude of time effects and time-by-treatment arm interaction effects detectable with a .80 power will range from $.27$ to $.18$, also respectively, which are medium-sized standardized effects. Thus, the study is underpowered to detect any but large differences

between the treatment arms and medium-sized or larger effects on time and time-by-treatment arm interactions. More important than the statistical comparisons, though, the analyses will yield key descriptive characterizations of the treatment-arm effects at the two posttest points (i.e., means, medians, proportions, and variances) on key outcomes, as well as effect size estimates that can be used in planning a larger scaled efficacy trial of the PIE intervention.

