6.4.3.1 Primary Analyses

The primary objective of this study is to examine whether the novel PIE intervention transforms parent-infant transactions over time as intended, thereby facilitating increases in the time infants spend in dyadic engagement with their parents. We will also evaluate whether dyadic engagement outcomes differ based on whether parents are coached first in the sensory reactivity domain followed by coaching in the prelinguistic communication domain, or are coached in the opposite order.

Specifically, we will estimate the separate and combined effects of the two PIE intervention domains on dyadic engagement (primary outcome). H1a: At Posttest-1, dyads coached in either PIE domain will exhibit moderately more dyadic engagement compared to Baseline (Cohen's $d \geq .40$). H1b: At Posttest-2, dyads in both study arms will show additional small to moderate increases in dyadic engagement compared to Posttest-1 (Cohen's $d \geq .25$).

Our primary analysis will be conducted to explore a priori contrasts of interest within using repeated measures within a mixed modeling framework. Of key interest will be the contrast of Baseline to Posttest-1 scores and the contrast of Baseline to Posttest-2 scores (time effect). In addition, the model will include terms for treatment arm effects and treatment arm-by-time interactions. A time effect will indicate growth in the outcome from baseline to the posttest point, a zero or negligible time effect indicates stability, and a negative time effect suggests a drop in scores. A non-negligible treatment arm effect indicates that the two treatment arms differ on the outcome; while a non-negligible interaction coefficient suggests that the magnitude of change from baseline to the posttest point are not equivalent for members of the 2 treatment arms. Since the primary outcomes are proportions, arc sin transformations of these proportions will be performed before entering them into the models.

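### Does H3b, which predicts no difference between arms in parent responsiveness at Posttest-2, need a stated margin or decision rule?

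*Combined protocol and SAP*

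**What the plan says.** H3b concerns two secondary outcomes: the project-developed ratings of parent responsiveness to sensory reactivity cues and to prelinguistic communication cues. It predicts that at Posttest-2 "there will be no between-arm differences in parent responses attuned to infant sensory reactions or prelinguistic communication leads", and it attributes this to gains in whichever domain was coached second.

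For the analysis, 6.4.3.2 refers Objective 3 back to Objective 2: "We will examine the contrast of Baseline to Posttest-1 scores and the contrast of Baseline to Posttest-2 scores (time effect"), plus arm and arm-by-time terms in a repeated measures mixed model.

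Four other places bear on how H3b would be read:

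- Section 6.4.1 plans, at Posttest-2, to "evaluate whether there are any effects of the order of coaching by comparing dyads in Arm1 to those in Arm2".
- Section 5.2.2 says that for these ratings the team wants to know "whether there are order effects (differences between study arms) at Posttest 2".
- Section 6.4.3.1, whose framework Objectives 2 and 3 share, reads results by size: "A non-negligible treatment arm effect indicates that the two treatment arms differ on the outcome". It gives no value for negligible.
- Section 6.4.2 concedes "Thus, the study is underpowered to detect any but large differences" between the arms, and then states its priority: "More important than the statistical comparisons, though, the analyses will yield key descriptive characterizations of the treatment-arm effects at the two posttest points".

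**The concern.** H3b is the only hypothesis that predicts no difference between arms. H1a, H1b, H2a, H2b and H4a each carry a Cohen's d bound; H3b has none. For a hypothesis that predicts a difference, low power is a handicap that the sponsor accepts. For one that predicts no difference, low power makes apparent agreement more likely if a non-significant test is taken as agreement.

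A moderate order effect that the trial missed could then be reported as evidence that parents end equally responsive whichever domain is coached first. Section 3.2 says order effects would inform redesign of the intervention, so a false reassurance would have some consequence.

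**Working it through.** **Inputs.** From 6.4.2: 40 dyads with complete data, 20 per arm; type I error .05; power .80; correlation among repeated measures r = .3 to .7. Assumptions: two-sided tests, normal outcomes, equal variances, complete data. The documents give no SD for the ratings, so differences are in SD units.

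**The plan's own figures.** With N = 40 and m = 2 occasions, the noncentrality for the arm effect is f² × N × m / (1 + (m − 1)r). For time and interaction it is f² × N × m / (1 − r).

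- Arm, r = .3: .3665² × 80 / 1.3 = 8.27
- Arm, r = .7: .4191² × 80 / 1.7 = 8.27
- Time or interaction, r = .3: .2689² × 80 / .7 = 8.26
- Time or interaction, r = .7: .1761² × 80 / .3 = 8.27

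Each gives 80% power on 1 and 38 df. The values round to the stated .37, .42, .27 and .18, so 6.4.2 reproduces.

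**Precision of the Posttest-2 arm difference.** The standard errors are:

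- Posttest contrast: √(2/20) = .316
- Change score (the arm-by-time term at Posttest-2): √(4(1 − r)/20) = .374, .316, .245 for r = .3, .5, .7
- Baseline-adjusted: √(2(1 − r²)/20) = .302, .274, .226. This is not the stated default, because 6.4.4 first runs models without covariates.

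The 95% half-width is the standard error times t, for example 2.024 × .316 = .640 on 38 df. Power comes from the noncentral t. The last two columns give the share of trials, at a true difference of zero, in which the 90% interval lies inside the margin (400,000 simulated trials). Neither margin is in the documents.

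| Analysis | 95% half-width (SD) | True 0.5 SD non-significant | Within ±0.50 SD | Within ±0.80 SD |
|---|---|---|---|---|
| Posttest | .64 | 66% | 3% | 60% |
| Change score, r = .3 / .5 / .7 | .76 / .64 / .50 | 74 / 66 / 49% | 0.2 / 3 / 28% | 35 / 60 / 88% |
| Baseline-adjusted, r = .3 / .5 / .7 | .61 / .55 / .46 | 63 / 57 / 42% | 5 / 14 / 40% | 66 / 78 / 93% |

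**What the figures show.** An observed difference of zero would typically leave open differences above the d = .40 that the protocol calls moderate for change over time. A non-significant result is therefore weak evidence for H3b. But a formal equivalence rule would rarely be met at 0.50 SD, and could be met reliably only at a margin wide enough to include large differences. On the posttest contrast, 80% power needs about 69 per arm at 0.50 SD and 275 at 0.25 SD.

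**Does the text commit the error?** No passage equates non-significance with support. The estimate is largely settled: H3b names the comparison and the time point, and 5.2.2 and 6.4.1 name them again. What is left open is the value of negligible, and whether the arm difference at Posttest-2 or the arm-by-time term is read.

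**The case for a change.** The strongest case for a change is that it costs one sentence. The plan does not say that non-significance will be read as support, but it does not exclude it either, and H3b remains a listed hypothesis on outcomes whose order effects are of declared interest. Section 6.4.3 gives priority to not overlooking signals, and taking a missed arm difference as agreement with H3b would be an oversight of that kind.

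Much of this stands. The planned contrasts can contradict H3b but cannot establish it, and a sentence saying so would do no harm. Two limits apply. First, the sample of 20 per arm is not the reason: without a margin no sample size would suffice, and with a wide enough margin 20 per arm could suffice. Second, the sentence would mostly write down what 6.4.2 already says, and nothing in the documents supplies a between-arm margin to put in it. The d < .25 bounds in H2a and H4a concern change over time.

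A related gap also stands. The second clause of H3b attributes the result to gains in the newly coached domain. That is a change from Posttest-1 to Posttest-2, in a different domain for each arm, and the listed time contrasts from baseline do not isolate it. The same mixed model yields that contrast directly if the team wants it.

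**Conclusion.** The observation is correct, but it is a missing detail that analysts fill sensibly, and no change to the plan is needed. The trial is a proof of concept; section 6.2.1 says it lacks the controls for an efficacy evaluation, and 6.4.2 puts effect sizes first. In keeping with that, the report would give each rating's Posttest-2 arm difference with its confidence interval and describe H3b as unresolved wherever the interval is wide.

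The interval will be wide: a half-width of about .64 SD on the posttest contrast, and .50 to .76 SD by change score as r falls from .7 to .3. These figures assume 20 complete dyads per arm and normal ratings with equal variances. The conclusion that no change is needed rests on the plan's silence about non-significance and on its stated preference for estimates; it would not hold if the results were reported as showing that coaching order makes no difference because p exceeded .05.

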For infants whose screening scores on the FYIv3.1b meet the threshold for being at elevated likelihood for a later diagnosis of an ND, the research coordinator will call the parents to further screen for infant and parent eligibility, offer information about the study, and invite families with no exclusionary factors to participate in a baseline assessment (with informed consent).

At baseline assessments, eligible infants will have a score of at least 1 standard deviation below the mean on the Receptive or Expressive Language scale (or both) of the Mullen Scales of Early Learning, as well as meeting clinically-determined criteria for elevated patterns of hypo-reactivity or hyper-reactivity (or both) on the Sensory Processing Assessment: "HYPO": Cut-point (equal or greater than) of 1.69 for Mean of the raw orienting score across 7 items, each with the range of 1 to 4 possible points). "HYPER": Cut-point (equal or greater than) of .333 for Mean of the raw approach/avoid novel toys score across 9 items, each with the range of 0 to 2 possible points) OR Any clear "defensive" response on orienting items or "Yes" to covering ears to sound (in stereotypies checklist). These inclusion criteria will ensure that infants are demonstrating delays or differences in areas of development that are targeted by the PIE intervention (sensory reactivity and communication).

Infants will include both sexes, although based on previous studies, we expect a 2:1 (male:female) ratio, given that boys are more likely to score at elevated likelihood for NDs (e.g., autism) targeted by the FYI.

Exclusion criteria: Infants with known genetic conditions (e.g., Down syndrome), and those with significant uncorrected vision/hearing/physical impairments will be excluded. We exclude infants with known genetic disorders due to our focus on testing PIE with infants at elevated likelihood of neurodevelopmental disorders based on behavioral markers, but whose eventual diagnosis remains unclear. We will exclude infants with significant uncorrected vision/hearing/physical impairments because they likely would not be able to fully participate in the assessment procedures, and the assessment results would be of questionable validity. Families who do not speak English as their primary language in the home (>50% of the time) will be excluded, because screening tools, assessments, and interventions are not available uniformly in other languages.

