5.3.2 Eligibility Criteria/Vulnerable Populations

Eligibility

1. Infant is between 11 and 16 months (inclusive) at the time that the parent completes the FYIv3.1b.
2. Infant scores at or above threshold on the FYIv3.1b for being at elevated likelihood for a later ND diagnosis.
3. Infant scores 1 SD below the mean on the Receptive Language and/or the Expressive Language Scale of the Mullen Scales of Early Learning.
4. Infant meets clinical criteria for elevated hypo- or hyper-reactivity on the Sensory Processing Assessment at the in-person baseline assessments.
5. A parent or other primary caregiver of the infant is available for study participation.
6. Family lives within the catchment area for the study.

Exclusion criteria

1. Infant has a known genetic conditions (e.g., Down syndrome).
2. Infant has a known significant uncorrected vision/hearing/physical impairments.
3. Family who do not speak English as their primary language in the home (>50% of the time).

Vulnerable populations:

This study will enroll participants from the vulnerable population of children. This study aims to provide intervention during infancy, before the full emergence of behavioral symptoms that would lead to a neurodevelopmental disorder diagnosis (e.g., ASD, language disorder, or attention deficit hyperactivity disorder). The underlying premises for the study require the participation of children: 1) The first 2 years of life are an especially active period of neural development. Due to rapid synaptic proliferation and experientially-

influenced shaping of functional connectivity, interventions initiated in infancy may be powerful in promoting more typical neural connectivity. (2) Biologically-based differences in infants at-risk for NDs lead to observable differences in sensory reactivity and communication behaviors in most infants by 11-16 months, prior to the full emergence of diagnostic symptoms. (3) Differences in infant behaviors influence the quantity and quality of parent responses. (4) Parent-child transactional processes begin early in infancy and impact long-term child outcomes.

Protections:

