6. The Mullen Scales of Early Learning provides 5 scales to assess development in children birth-68 months. Each scale (Gross Motor, Fine Motor, Visual Reception, Receptive Language, Expressive Language) yields a T-score, percentile and age equivalent. The MSEL scales have demonstrated good to strong internal consistency, test-retest reliability and concurrent validity; it has been widely used as a standardized measure of development across domains in studies of young children with NDs, including many previous studies by members of our team. Prior research indicates that receptive language may be improved distal to with improvements in parent-infant dyadic engagement and infant intentional communication. We will administer the Fine Motor, Visual Reception, Receptive Language, and Expressive Language Scales at Baseline to provide descriptive information across these developmental domain to characterize the developmental status of our sample. At Posttest-2, we will administer the Receptive and Expressive Language Scales only, as secondary outcome measures to determine whether the PIE intervention has distal effects on broader language outcomes of the infants.

In the age range for our infant participants, the estimated participant time required for the 4 scales of the MSEL at Baseline is 15-20 minutes. At Posttest-2, the estimated time to

administer the Receptive and Expressive Language Scales is 10 mintues.

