9. Sensory Processing Assessment for Young Children (SPA, [name], 1999a). In coaching parents to be sensitive to their infants' cues related to sensory reactivity and to respond in ways that support their infants' regulation of these responses, another potential distal outcome of the PIE intervention would be improvements in extreme patterns of sensory reactivity (i.e., diminished hypo- and/or hyper-reactivity). Use of the SPA as an

observational measure will provide us with the opportunity to assess whether any changes are observed by assessors who are blinded to the arm of the study to which families are assigned. The SPA is a play-based assessment that measures approach-avoidance to novel sensory toys, sensory seeking behaviors, and orienting responses across three sensory modalities, and is sensitive to maturational changes. It has good inter-rater reliability (ICC = .91 to .99 for different scales), discriminates different patterns of sensory response between children with autism and children with other developmental disabilities, and shows sensitivity to developmental changes ([name] et al., 2007, 2013).

The SPA will be administered at Baseline and Posttest-2. The participant time required for this measure is ~15 to 20 minutes.

10. Sensory Experiences Questionnaire v. 2.1, (SEQ, [name], 1999b). As a complement to the SPA, we are using the SEQ to determine whether parents perceive improvements in their children's sensory reactivity patterns over the course of the full PIE intervention. The SEQ is a 43-item questionnaire for children 6 months to 6 years that measures responses to various sensory stimuli in the context of daily activities. Factor scores for hypo- & hyper-responsiveness and sensory seeking are compatible with the conceptual model of the SPA. The internal consistency is acceptable (Cronbach's $\alpha = 0.80$). It discriminates patterns unique to ASD and is sensitive to maturational changes ([name] et al., 2006).

Parents will be asked to complete the SEQ at Baseline, Posttest-1, and Posttest-2, and completing it will require ~15 minutes.

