For children who meet final study eligibility criteria for the intervention trial based on baseline assessment results for the expressive and/or receptive language and sensory reactivity, the study coordinator will complete the written informed consent process at the end of the baseline assessment.

3. The assigned PIE intervention coach for each enrolled family will schedule an initial introductory visit with the family, which will include recording a 5-10 minutes video of parent-infant interaction to use in the first coaching session. This introductory visit will require a total of approximately 45-60 minutes.
4. Coaching in the first PIE domain for the family (randomly assigned) will take place in 6 weekly visits at the home of the dyad, lasting approximately one hour each.
5. Posttest-1 will occur after the conclusion of coaching in the first PIE domain at the study's office in Carrboro, NC. Total estimated time for dyads is 25-30 minutes, allowing for time for introductions and the infant to settle into the setting; parents will spend an additional 15 minutes completing a questionnaire at a location of their choice. The following assessments will be completed:
 - Parent-infant interaction session - 20 minutes
 - Sensory Experiences Questionnaire - 15 minutes (parents only; can be completed online, or in hardcopy form if parents prefer, from location of parent choice)
6. Coaching in the 2nd PIE domain will take place in 6 weekly visits at the home of the dyads, lasting approximately one hour each.
7. Posttest-2 assessments will take place at the study office in Carrboro, NC, and will last approximately 1.5 to 2 hours, allowing for introductions, transitions between assessment activities, breaks for the infant, and a brief concluding conversation with parents regarding the infant's developmental assessment results and recommendations, if appropriate, for community services. Parents will also complete two questionnaires requiring an additional 15-10 minutes, at the location of their choice.
 - Parent-infant interaction session - 20 minutes
 - Child-directed speech paradigm - 10 minutes

- Mullen Scales of Early Learning Receptive and Expressive Language Scales - 10 minutes
- Attention Following trials - 2 minutes
- Brief Observation of Social-Communication Change - 13 minutes
- Sensory Processing Assessment - 15 minutes

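### The Baseline MSEL language and SPA results that admit infants are also the starting values for H4b, so regression to the mean pushes the MSEL time effect slightly toward improvement, and usually the SPA one too

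*Combined protocol and SAP*

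**What the plan says.** **Entry.** Section 5.3 requires that at Baseline "eligible infants will have a score of at least 1 standard deviation below the mean on the Receptive or Expressive Language scale", or on both. Section 5.3.2 adds: "Infant meets clinical criteria for elevated hypo- or hyper-reactivity on the Sensory Processing Assessment at the in-person baseline assessments". The SPA rule in 5.3 joins a hypo cut-point (mean orienting score of 1.69 or more) and a hyper cut-point (mean approach/avoid score of .333 or more) by 'or'. It also admits on a clear defensive response or on "covering ears to sound (in stereotypies checklist". Section 6.3.1 confirms that eligibility is settled at the same visit, "based on baseline assessment results for the expressive and/or receptive language and sensory reactivity".

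**Outcome.** Section 5.2.2 lists MSEL language and SPA among the outcomes taken at Baseline and Posttest 2, and says that the size of change is of particular interest. Section 6.1.3 gives the purpose of the MSEL retest: "to determine whether the PIE intervention has distal effects on broader language outcomes of the infants". For SPA it says: "The SPA will be administered at Baseline and Posttest-2". Section 6.4.3.2 then states H4b, "Infants will demonstrate small improvements in language, sensory reactivity patterns, response to joint attention, and social-communication skills over the course of the PIE intervention", and analyses it with the mixed-model framework of the primary analysis, where 6.4.3.1 reads a time effect as growth.

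**Comparator.** Under 4.1 every dyad receives both PIE domains. No second pre-treatment measurement is scheduled, and regression to the mean is not mentioned.

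**The concern.** An infant who just passes a cut-off has, on average, a Baseline error in the direction that helped it pass. At Posttest-2 the error is drawn afresh, so the group mean moves back without any real change. On MSEL this appears as improvement. With no untreated arm, nothing subtracts it from the time effect.

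Two uses are at stake. First, H4b has no numeric threshold, unlike H1, H2 and H4a, so any significant positive time effect could be counted as support. Second, section 3.2 says that effect sizes from this study will guide later efficacy trials and does not set these pre-post values aside.

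**Working it through.** **1. The plan's own figure.** Section 6.4.2 gives detectable time effects of f = .27 to .18 (N = 40, power .80, alpha .05, correlation ρ of .3 to .7). With λ = f²·N·m/(1−ρ), on m−1 and 38(m−1) degrees of freedom, m = 2 timepoints gives f = .269 at ρ = .3 and .176 at ρ = .7. The figures reproduce. With two timepoints d = 2f, so the stated values mean d of about .54 to .36. The plan gives no figure for selection bias.

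**2. Inputs from the documents.** n = 40 analysed (6.4.2). Section 6.3.4 expects 57% of assessed infants to meet full inclusion criteria. That is language *and* SPA together, so the language criterion alone passes at least 57%. (The 49 of 84 printed there is 58.3%; I use the stated 57%.)

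**3. Assumptions.** If the two criteria are independent and equally strict, each passes √.57 = 75.5%. Retest correlation r is .7 to .9, because 6.1.3 gives no coefficient and says only "The MSEL scales have demonstrated good to strong internal consistency, test-retest reliability and concurrent validity". The correlation ρ between Receptive and Expressive scores is .4 to .7. Scores are normal and age-normed, with no true change. SD units are those of assessed infants, taken as equal to the normative SD.

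**4. Formula.** Let P be the language pass rate, c the cut-off in SDs from the assessed mean, φ the normal density and Q the upper-tail probability. Selection on either scale at or below c lowers each Baseline mean by

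m = (1+ρ)·A, where A = φ(c)·Q(c·√((1−ρ)/(1+ρ)))/P.

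The spurious gain on retest is

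- (1−r)·A if the errors of the two scales at a visit are independent;
- (1−r)·m if they are fully shared, as when an infant has a bad day.

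**5. Worked cell.** P = .755, ρ = .55, r = .8 gives c = .262, φ(c) = .385 and Q(.262 × .539) = .444. Then A = .385 × .444/.755 = .226 and m = 1.55 × .226 = .351. The gain is .2 × .226 = .045 SD (independent) or .2 × .351 = .070 SD (shared).

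**6. Range.** Simulation (four-variate normal, paired t-test on batches of 40) agrees with the formula. Ranges are over r and ρ as above; error is two-sided, against 5%.

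| Language pass rate | Gain, independent errors | Error | Gain, shared errors | Error |
|---|---|---|---|---|
| 57% (boundary) | .04–.12 SD | 8–15% | .05–.18 SD | 11–33% |
| 75.5% | .02–.07 SD | 6–9% | .03–.11 SD | 8–15% |
| 80% | .02–.06 SD | 6–8% | .03–.09 SD | 7–12% |

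Divided by the Baseline SD of enrolled infants, the 75.5% gains are d of about .03 to .14. Arm-by-time two-sided error stays at 4.7 to 5.2%, because both arms are selected in the same way before randomisation.

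**7. SPA, direction only.** The documents give no SPA retest coefficient (the ICC of .91 to .99 is inter-rater), and the categorical entry routes cannot be modelled from them. A check that ignores those routes used r of .7 to .9, true-score correlation −.3 to .3, within-visit error correlation −.6 to .6, and hypo/hyper pass rates of 50/50, 55/40, 55/10 and 10/55. Both scales moved toward improvement whenever the error correlation was zero or positive, and in every 50/50 and 55/40 case. Only at 55/10 or 10/55 with negatively correlated errors did the rarer scale move the wrong way, by up to .070 SD.

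**The case against.** **The limitation is disclosed.** Section 6.2.1 says that efficacy is not an aim and that the needed controls are absent, and 6.4.2 ranks description above testing. This stands as a general caveat and is a good reason to call the point minor. It does not name a directional bias that the entry rule creates on two particular instruments, and 6.1.3 and 6.4.3.1 still read the change as a distal effect or as growth. Section 6.4.3 also accepts more type I error, but in declining a multiplicity adjustment. That tolerates chance findings; it does not address a shifted estimate.

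**The effect is small and loosely anchored.** This largely stands. At 75.5% the d stays below the .25 that the plan itself calls limited in H4a, and far below the detectable d of .36 to .54. The pass rate and r are assumed. Section 6.1.3 lists T-score, percentile and age equivalent without saying which is analysed, and on an age-equivalent scale ordinary development would swamp the artefact. In the other direction, 6.4.2 uses correlations of .3 to .7 for repeated measures in general. The bias is proportional to 1−r, so r = .5 with shared errors at 75.5% would give up to .5 × .373 = .19 SD. I keep .7 to .9 because of the reliability statement in 6.1.3.

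**The planning harm is indirect.** Section 6.4.2 ties the planning output to arm effects at the two posttests, which are unbiased here. This stands in part: 3.2 is broader and excludes nothing, but the documents do not state that a pre-post d on MSEL or SPA will be used.

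**Conclusion.** The point holds as a minor one. The MSEL language time effect is biased toward improvement by construction, probably by about .02 to .11 SD, with two-sided error of 6 to 15% in place of 5%, under the assumptions in the working. Within them it is larger only near the 57% boundary.

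A reader might infer more than the documents support:

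- *That H4b would be met by artefact alone.* The 33% error rate needs every language-qualifying infant to pass SPA as well, together with r = .7 and fully shared errors. Elsewhere the artefact is a small part of any change large enough to detect reliably.
- *That SPA is inflated by a known amount.* Its size cannot be computed, and on one scale the direction can reverse.
- *That the randomised comparison is compromised.* Arm and arm-by-time contrasts are unbiased in expectation.
- *That every H4b measure is affected alike.* Joint attention, BOSCC and SEQ do not decide entry and are touched only through their correlation with the measures that do.

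**What to change.** Keep the planned models and report the estimates. Add to 6.4.3.2, Objective 4:

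> Baseline MSEL language and SPA scores determined eligibility, so their Baseline-to-Posttest-2 change includes regression to the mean. A time effect on these measures will be reported descriptively with this label and will not by itself be read as growth (6.4.3.1) or as a distal effect of PIE (6.1.3). Its unadjusted pre-post d will not be used as an intervention effect size in planning the efficacy trial.

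This needs no new data and no new analysis. The cost is that an MSEL or SPA time effect can no longer stand alone as evidence of a PIE effect. For language and observed sensory reactivity, that part of H4b becomes descriptive.
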